5.2. Sample Size and Power

Assuming a placebo-adjusted treatment effect size of 0.75 ([Burdick 2014](#); the estimated treatment difference in z-score was 0.8 with a standard deviation of 1.07) in the WAIS-IV Coding test, a total sample size of 60 evaluable participants (30 per arm) will provide 80% power at a two-sided significance level $\alpha=0.05$.

Adjusting for an anticipated 20% dropout rate, approximately 76 participants will be randomly assigned in a 1:1 ratio to either SAGE-718 or placebo.

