6. MODIFICATIONS

6.1. Modifications from the Approved Clinical Study Protocol

- Protocol does not specify the analysis objective of Daily (Mobile Phone-based) Assessments including Psychomotor Vigilance Task (PVT), Digit Symbol Substitution Test (DSST), and National Sleep Foundation Sleep Diary. They will be analyzed to evaluate the below objectives.
 - PVT: To evaluate the effect of SAGE-718 on motor symptoms in participants with PD-MCI.
 - DSST: To evaluate the effect of SAGE-718 on additional measures of global and domain-specific cognitive performance in participants with PD-MCI.
 - National Sleep Foundation Sleep Diary: To evaluate the effect of SAGE-718 on functioning in participants with PD-MCI.
- Protocol Section 10.6.1: [REDACTED]
- Protocol Section 11.3.2.2: [REDACTED]

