8.3.1.2.13. Daily (Mobile Phone-Based) Assessments

Daily assessments will be derived for Baseline, Day 14, and Day 42 using the mean of non-missing assessments for 7 days as described in the [Table 2](#) below. The baseline measurement will be calculated as the mean of days immediately preceding to first dose day. The precision level of averages is to keep one decimal place. [Table 2](#) lists visit deviation. If there are missing assessments for more than 4 days among 7 days, the derived mean will be considered as missing.

Table 2. Analysis Visit Derivation for Daily Mobile Assessments

Scheduled Visit	Derivation for averaging
Baseline *	> Day -7 and \leq Day 1
Day 14	> Day 7 and \leq Day 14
Day 42	> Day 35 and \leq Day 42

* Day 1 assessment will be collected prior to the first dosing per protocol. For PVT and DSST, if Day 1 assessment is collected after the first dose or not available, available non-missing assessments for 7 days prior to the first dose will be used (i.e., > Day -8 and \leq Day -1).

8.3.1.2.13.1. Psychomotor Vigilance Task

The PVT has participants press a button in response to a simple visual stimulus provided at random intervals. The primary measure is the number of missed responses, which describes the participant's sustained attention. This test will be administered each morning during the Treatment Period using a mobile device. At scheduled clinic visits, the task will be performed in the clinic under observation by study staff, otherwise the participant will perform this task remotely (at home).

The key outcome measures are:

- PVT Total False Positives
- PVT Total Timeouts
- PVT Slope of Linear Fit
- PVT Reaction Latency (mean)
- PVT Reaction Latency (Coefficient of Variation)
- PVT Total Hits

Other outcome measures are:

- PVT Reaction latency (variance)
- PVT Mean Press Length

8.3.1.2.13.2. Digit Symbol Substitution Test

The DSST is widely used to monitor changes in cognitive function over time and for early detection of cognitive dysfunction. The task requires participants to use a reference key to pair specific numbers with geometric figures. The number of correct pairings achieved within 90 seconds is summed to generate a total score. This test will be administered each morning during the Treatment Period using a touch screen mobile device. At scheduled clinic visits, the task will be performed in the clinic under observation by study staff, otherwise the participant will perform this task remotely (at home).

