The key outcome measures are:

- DST Total Correct
- DST Total Incorrect
- DST Correct Movement Latency Mean
- DST Incorrect Movement Latency Mean
- DST Correct Response Latency Mean
- DST Incorrect Response Latency Mean

Other outcome measures are:

- DST Correct Movement Latency SD
- DST Incorrect Movement Latency SD
- DST Correct Response Latency SD
- DST Incorrect Response Latency SD

8.3.1.2.13.3. National Sleep Foundation Sleep Diary

Once daily in the morning, participants will briefly answer 5 questions about sleep length, sleep latency, night awakenings, and sleep quality. These questions have been modified from version 6 of the National Sleep Foundation Sleep Diary. This diary will be completed each morning during the Treatment Period using a mobile device. At scheduled clinic visits, the task will be performed in the clinic under observation by study staff, otherwise the participant will perform this task remotely (at home).

Outcome measures are individual items for sleep length, sleep latency, night awakenings, and sleep quality. Sleep length (minutes) is computed as participant get out of bed this morning – time participant went to bed last night. There is no key outcome measure.

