8.3.3. Analysis of Primary Efficacy Variable

8.3.3.1. Primary Analysis

Participants will be analyzed according to randomized treatment. Descriptive statistics of WAIS-IV Coding test score, percent change from baseline and change from baseline will be summarized by treatment group and by visit.

The primary endpoint is change from baseline to Day 42 in the WAIS-IV Coding test and this primary endpoint will be analyzed using a mixed-effects model for repeated measures (MMRM). The model will include baseline WAIS-IV Coding test score as a continuous explanatory variable, treatment, visit, and visit-by-treatment interaction as categorical explanatory variables. The Kenward-Roger correction to degrees of freedom will be applied. All explanatory variables will be treated as fixed effects in the model, and all post-baseline time points will be included in the model. An unstructured (UN) covariance matrix with the default Newton-Raphson algorithm used by SAS PROC MIXED will be used to model the within-subject correlation. If this model fails to converge – or, if the convergence criteria is met but the final Hessian is not positive definite - the Fisher Scoring algorithm (via the SCORING option of the PROC MIXED statement), the no-diagonal factor analytic structure (via the TYPE=FA0(T) option of the REPEATED statement, where T is the total number of time points), Toeplitz, Autoregressive (1) [AR (1)], Compound symmetry (CS) covariance structure will be used, following this sequence until convergence is achieved. If the model still does not converge with CS structure, no results will be reported. When the covariance structure is not UN, the sandwich estimator for the variance-covariance matrix will be derived, using the EMPIRICAL option in the PROC MIXED statement in SAS. The primary comparison will be between SAGE-718 and placebo at the Day 42. LSM and SE with 95% CI for each treatment group as well as difference in LSM and SE with 95% CI will be summarized, and the p-value from the hypothesis test of no difference between the treatment groups will be also presented.

Line plots with LSM and SE bars of change from baseline in WAIS-IV Coding test score over time by treatment group will be provided.

By-participant listing of WAIS-IV Coding test score by treatment group and by visit will be produced.

8.3.3.2. Multiplicity adjustment:

Not applicable.

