8.3.4.14. Daily (Mobile Phone-Based) Assessments

For PVT and DSST, invalid data will be flagged after science team review by the vendor and will not be used for the analysis.

For key outcome measures specified in [Section 8.3.1.2.13](#), the change from baseline to Day 14 and Day 42 will be summarized using descriptive statistics and analyzed using a similar MMRM model described in [Section 8.3.3.1](#). A plot showing the LSM \pm SE bar over time within each treatment group will also be provided.

Other outcome measures specified in [Section 8.3.1.2.13](#) will be summarized by visit using descriptive statistics.

By-participant listing by visit will be provided.

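### The key DSST error outcome is a count from a fixed 90-second test with no denominator, so on its own it cannot separate accuracy from speed

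*SAP*

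**What the plan says.** SAP 6.1 gives the DSST its purpose: "DSST: To evaluate the effect of SAGE-718 on additional measures of global and domain-specific cognitive performance in participants with PD-MCI". SAP 8.3.1.2.13.2 describes the scoring: "The number of correct pairings achieved within 90 seconds is summed to generate a total score". Six key outcomes follow, among them "DST Total Correct" and "DST Total Incorrect"; the other four are mean movement and response latencies for correct and incorrect responses. The remaining DSST outcomes are the SDs of those latencies.

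The value analysed at each visit is a window average: "Daily assessments will be derived for Baseline, Day 14, and Day 42 using the mean of non-missing assessments for 7 days". The same paragraph of 8.3.1.2.13 keeps averages to one decimal place and treats a window as missing if more than 4 of its 7 days are missing.

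For the key outcomes, SAP 8.3.4.14 states that "the change from baseline to Day 14 and Day 42 will be summarized using descriptive statistics and analyzed using a similar MMRM model", referring to SAP 8.3.3.1. That section says: "The model will include baseline WAIS-IV Coding test score as a continuous explanatory variable, treatment, visit, and visit-by-treatment interaction as categorical explanatory variables". For the DSST the natural reading is that each outcome's own baseline takes the place of the Coding score. Nothing in the model refers to the number of items attempted. Neither DSST list contains an error proportion, a percent correct or a total attempted.

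**The concern.** In a fixed-time test the number of items attempted depends on speed, and an error can occur only on an attempted item. A count of incorrect responses therefore mixes how fast a participant works with how often each response is wrong. A drug meant to improve cognition should raise items attempted. If it does so and leaves accuracy alone, the error count moves in the unfavourable direction. If it improves both, the two effects pull the count in opposite directions and may cancel. The reverse also holds: slowing down at the same accuracy lowers the count and looks like an improvement.

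At stake is the reading of one key DSST outcome, which is reported with a treatment difference and a p-value. The primary endpoint and the sample size are not affected.

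**Working it through.** **The plan's own figure.** SAP 5.2 bases the effect size on this: "the estimated treatment difference in z-score was 0.8 with a standard deviation of 1.07". 0.8 / 1.07 = 0.748, rounded to 0.75. A two-sample t test with 30 per arm at two-sided 0.05 has power of 81.3% (effect 0.748) to 81.5% (effect 0.75). 60 / 0.8 = 75, or 76 as 38 per arm. The stated design reproduces. The documents give no planning figure for any DSST outcome.

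**Arithmetic that needs no assumed pace or error rate.** Let A be items attempted in 90 seconds and e the error probability per item.

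- Expected incorrect count = A × e.
- Speed up by a fraction g, accuracy unchanged: A(1 + g)e, a relative rise of exactly g for any A and any e above zero.
- The count stays unchanged when e falls to e / (1 + g), so the hidden relative fall is 1 − 1/(1 + g): 9.1% for g = 10%, 16.7% for g = 20%, 23.1% for g = 30%.

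Example with A = 40, e = 5%, g = 20%: incorrect 40 × 0.05 = 2.0 becomes 48 × 0.05 = 2.4, and correct 38.0 becomes 45.6. Accuracy is 95% both times.

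**Size under assumed pace (not in the documents).** Take mean/SD of items attempted as 30/8, 35/10 and 45/10, and borrow the plan's 0.75 SD:

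| Mean/SD | 0.75 SD in items | Rise in attempts, hence in errors | SD for a 10% rise |
|---|---|---|---|
| 30/8 | 6.0 | 20.0% | 3.0/8 = 0.375 |
| 35/10 | 7.5 | 21.4% | 3.5/10 = 0.35 |
| 45/10 | 7.5 | 16.7% | 4.5/10 = 0.45 |

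At error rates of 3% and 6% this is between 6.0 × 0.03 = 0.18 and 7.5 × 0.06 = 0.45 extra errors per test.

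**Simulation A.** The three pairs above, each at error rates of 3% and 6%. Further assumptions: 30 per arm, 7 daily tests per window, between-person CV of error rate 0.6, day-to-day SD of attempts 3, and change regressed on treatment and baseline; 1,000 trials per setting.

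- Speed gain of 0.75 SD, accuracy unchanged: significant rise in the count in 26-56% of trials (below half in five of six settings); significant rise in the error proportion in 2-3%.
- Same speed gain with a true 20% relative fall in error rate: improvement detected by the count in 3-12%, by the proportion in 32-73%.

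**Simulation B.** Mean 40 attempts (SD 8), log-SD of error rate 0.5, 5% random change in pace, 30 per arm, 7 tests, 2,000 runs. Entries are the share of runs with two-sided p < 0.05:

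| Error rate | Count, +20% speed only | Proportion, +20% speed only | Count, +20% speed and −16.7% error rate | Proportion, same |
|---|---|---|---|---|
| 2% | 25% | 4.4% | 4.4% | 23% |
| 5% | 49% | 4.6% | 5.0% | 49% |
| 10% | 74% | 4.8% | 5.6% | 78% |

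The two simulations use different assumptions and agree in direction.

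**The case against.** The SAP never calls Total Incorrect an accuracy or error-rate measure. Read as a count it is estimated correctly, since a faster participant at fixed accuracy does make more errors in 90 seconds. This stands, and it is why the point concerns what the count can show and is not a claim that it is miscalculated.

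The strongest argument is that the safeguard is already present. All six key outcomes are planned for one table (Appendix E, Table 14.2.4.6.1), so a speed gain would show in Total Correct and in the latencies. In a rerun of simulation A, no trial showed a significant rise in the count without a significant rise in Total Correct. That model has no lasting random change in pace, which flatters Total Correct, but the argument largely stands. It warns the reader that speed has changed. It does not supply an estimate of accuracy, and it does not recover an accuracy gain that speed has cancelled.

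The sizes are fragile. The 0.75 SD belongs to a 120-second paper-and-pen test and is borrowed here for a 90-second touch-screen test. The SAP accepts windows with as few as 3 tests; with 3, the 26-56% falls to 15-33%. With a gain of 0.38 SD and 7 tests it is 11-19%.

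Scoring is also undefined. The 90-second rule is stated for correct pairings, and nothing says whether repeated attempts at one item each count as incorrect.

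A reader might infer that the plan will report a drug that only speeds participants up as harming accuracy, or that a trial conclusion rests on this p-value. The documents support neither. Significance in the unfavourable direction occurs in only some simulated trials, the DSST is assigned to additional measures, and no decision rule uses the result.

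**Conclusion.** The point holds as a limited, inexpensive improvement. A key DSST outcome is an error count in fixed time, tested without regard to items attempted, and no readable DSST outcome gives errors per item. The direction follows from arithmetic for any non-zero error rate that does not change with speed: the count rises by the speed gain, and a 20% gain hides a 16.7% relative fall in error rate. The frequency of a significant rise, about 26-56% of trials at 0.75 SD with 30 per arm and 7 daily tests, rests wholly on assumed pace, spread and error rates. All of this takes the outcome's name and the 90-second rule to mean a plain count of incorrect responses. The primary analysis is untouched.

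**What to change.** In SAP 8.3.1.2.13.2, add as the key accuracy outcome: DST percent incorrect = 100 × sum of Total Incorrect / sum of (Total Correct + Total Incorrect), over the valid tests in each 7-day window, analysed with the same MMRM. State two exceptions for this variable in 8.3.1.2.13:

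- The pooled percentage replaces the mean of daily values.
- The one-decimal rounding does not apply. If the outcome were left as a proportion, values of 0.03 to 0.06 would round to 0.0 or 0.1; in simulation this cut detection of a true accuracy gain from 35-75% to 14-33%.

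Summarise Total Incorrect descriptively, or at least state that it is interpreted only alongside the percentage. Leave Total Correct unchanged. One sentence on how Total Incorrect is scored would settle the remaining ambiguity.

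The cost is SAP wording and one derived variable from two counts already collected, with no new data. The downside is that the raw count would no longer be the tested error measure.

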8.3.2. Visit Windows for Efficacy Analyses

The scheduled visits will not be windowed and will be used at nominal visit value for analysis purposes. The unscheduled and ET visit will be mapped to a scheduled visit for analysis. In order to accommodate as much data as possible into analysis, the executive windows have been defined as shown in below tables, which have been widened, compared to protocol-specified operational windows. These windows will be used for analysis purposes only. Once analysis visit windows are assigned, all visits, including scheduled visits, unscheduled visits, and ET visits will be eligible for being flagged as the "analyzed record" within the analysis window; a participant's individual analysis visit window could potentially contain more than 1 visit. In the event of multiple visits falling within an analysis window or in case of a tie, the following rules will be used in sequence to determine the "analyzed record" for the analysis visit window:

- If the data from the scheduled visit is available, then the scheduled visit data will be used.
- If no data from the scheduled visit is available, the data from unscheduled visit closest to the scheduled study day for that window will be used.
- If there is a tie before and after the scheduled day, the later data will be used.

Table 3. Analysis Visit Windows for WAIS-IV Coding Test, [REDACTED]

Scheduled Visit (+/-1 window days) in protocol	Target Study Day	Study Day Window for Visit in Analysis
Baseline	Day 1 (pre-dose)	Day 1 (pre-dose) or last non-missing assessment before the first dose of IP
Day 14 (± 2 days)	Day 14	Day 2 – Day 28
Day 42 (-2 days)	Day 42	Day 29 – Day 56
Day 70 (± 4 days)	Day 70	Day 57 – End of study

[REDACTED]

[REDACTED]
[REDACTED]

[REDACTED]
[REDACTED]

[REDACTED]
[REDACTED]

8.3.3. Analysis of Primary Efficacy Variable

8.3.3.1. Primary Analysis

Participants will be analyzed according to randomized treatment. Descriptive statistics of WAIS-IV Coding test score, percent change from baseline and change from baseline will be summarized by treatment group and by visit.

The primary endpoint is change from baseline to Day 42 in the WAIS-IV Coding test and this primary endpoint will be analyzed using a mixed-effects model for repeated measures (MMRM). The model will include baseline WAIS-IV Coding test score as a continuous explanatory variable, treatment, visit, and visit-by-treatment interaction as categorical explanatory variables. The Kenward-Roger correction to degrees of freedom will be applied. All explanatory variables will be treated as fixed effects in the model, and all post-baseline time points will be included in the model. An unstructured (UN) covariance matrix with the default Newton-Raphson algorithm used by SAS PROC MIXED will be used to model the within-subject correlation. If this model fails to converge – or, if the convergence criteria is met but the final Hessian is not positive definite - the Fisher Scoring algorithm (via the SCORING option of the PROC MIXED statement), the no-diagonal factor analytic structure (via the TYPE=FA0(T) option of the REPEATED statement, where T is the total number of time points), Toeplitz, Autoregressive (1) [AR (1)], Compound symmetry (CS) covariance structure will be used, following this sequence until convergence is achieved. If the model still does not converge with CS structure, no results will be reported. When the covariance structure is not UN, the sandwich estimator for the variance-covariance matrix will be derived, using the EMPIRICAL option in the PROC MIXED statement in SAS. The primary comparison will be between SAGE-718 and placebo at the Day 42. LSM and SE with 95% CI for each treatment group as well as difference in LSM and SE with 95% CI will be summarized, and the p-value from the hypothesis test of no difference between the treatment groups will be also presented.

Line plots with LSM and SE bars of change from baseline in WAIS-IV Coding test score over time by treatment group will be provided.

By-participant listing of WAIS-IV Coding test score by treatment group and by visit will be produced.

8.3.3.2. Multiplicity adjustment:

Not applicable.

8.3.3.3. Sensitivity Analysis of Primary Endpoint

If any of the sensitivity analyses yields a result that is in a different direction from the result of the primary analysis, the nature of the discrepancy will be examined to clearly explain the discrepancy based on statistical principles and discrepancy will be discussed in the CSR.

8.3.3.3.1. Control-Based Pattern Mixture Model Multiple Imputation

If $\geq 10\%$ of participants have missing data in the primary endpoint, a sensitivity analysis using control-based Pattern Mixture Model Multiple Imputation (PMM-MI) under the missing not at random (MNAR) assumption will be used to investigate the impact of missing data (Lingling 2019, SAS Institute Inc.). MNAR assumes the missingness depends on the unobserved study data and cannot be predicted solely based on participant's observed data.

In cases where there is a missing baseline value, the missing baseline value will not be imputed with control-based PMM-MI. Instead, the average of all available baseline values (regardless of treatment group) will be populated for the missing baseline value. After this step, the control-based PMM-MI will be applied. Control-based PMM-MI under MNAR involves four steps as described below.

Step 1. Assessing the pattern of missing data.

To investigate the pattern of missing data, "ods output misspattern" will be used in the MI procedure of the SAS system (PROC MI). The imputation method will be based on the observed pattern of missing data and amount of missing data. The pattern of missing data will be assessed as monotone or arbitrary.

Step 2. Turning the arbitrary missing patterns to monotone missing patterns under missing at random (MAR) assumption.

If a mixture of non-monotone and monotone missing patterns exist in the data with majority of monotone missing patterns, then the arbitrary missing patterns will be converted to monotone missing patterns under MAR assumption.

Step 3. Generation of imputed datasets for AVAL using control-based pattern imputation under MNAR.

PROC MI will be used to generate m complete datasets. The selection of m depends on the required computing time and will be determined based on the amount of missing information prior to the last patient last visit but has been recommended varying from 5 to 100.

Step 4. Convert datasets into long format in which CHG variable represents all change from baseline with different values of avisit.

Step 5. Conducting model-based analysis using each imputed dataset.

The m complete datasets are analyzed using MMRM.

Step 6. Pooling the results from the imputed m datasets for inference.

The results from the m complete datasets are combined to produce inferential results.

8.3.3.3.2. Tipping Point Analysis

If $\geq 10\%$ of participants have missing data in the primary endpoint, another sensitivity analysis – tipping point analysis – will be considered to investigate the robustness of the result to departures from the MAR assumption of the MMRM model and to identify the tipping point

where the treatment effect in participants with missing data overturns the treatment effect from statistically significant to statistically non-significant.

Hence the tipping point analysis will only be performed if the primary efficacy analysis is statistically significant in treatment effect.

Implementing the tipping point approach includes the following steps ([Yuan 2014](#), [SAS Institute Inc.](#)):

Step 1. Missing baseline will be imputed as the mean of non-missing baseline for all other participants. For post-baseline, under the MNAR assumption, missing WAIS-IV Coding test score up to Day 70 will be imputed using PROC MI under MNAR.

Step 2. The imputed values for observations in SAGE-718 treatment group will be adjusted directly using the shift parameter (δ).

Step 3. The imputed datasets with the shift parameter applied will be analyzed using PROC MIXED.

Step 4. The results will be combined for the inference using PROC MIANALYZE.

Step 5. Step 1-4 will be repeated until the result is not statistically significant.

Step 6. If needed, step 1-5 will be repeated with more stringent shift parameter applied until the result is not statistically significant.

The shift parameter (δ) value will be progressively decreased, and process repeated until non-significant p-value is achieved. One hundred datasets will be generated.

The tipping point summary for each pairwise comparison will include LSM difference, the 95% CI, and p-value for each of δ value. Iterations including the tipping point will be summarized.

